#### 4.2. Exclusion Criteria

- 1. Prior therapy with anti-PD-L1 and anti-PD1 antibodies, MEK inhibitors or MDM2 antagonists.
- 2. No more than 3 lines of chemotherapy in the metastatic setting
- 3. No concurrent anticancer therapy. Required washout from prior therapy:
  - Endocrine therapy: no required wash-out
  - Chemotherapy: 14 days
  - Major surgery: 14 days (provided wound healing is adequate)
  - Radiation: 7 days
  - Investigational/Biologic Therapy (half –life ≤ 40 hours): 14 days
  - Investigational/Biologic Therapy (half –life > 40 hours): 28 days
  - Use of corticosteroids or immunosuppressive medication is exclusionary, except the following in the absence of active autoimmune disease:
    - Subjects are permitted the use of corticosteroids with minimal systemic absorption (e.g. topical, ocular, intra-articular, intranasal, and inhaled);
    - Systemic corticosteroids at physiologic doses ≤10 mg/day of prednisone or equivalent are permitted;
    - Adrenal replacement steroid doses including doses > 10 mg daily prednisone are permitted;
    - A brief (less than 3 weeks) course of corticosteroids for prophylaxis (e.g. CT scan premedication against contrast dye allergy) or for treatment of non-autoimmune conditions (e.g. delayed-type hypersensitivity reaction caused by a contact allergen) is permitted.
- 4. Previous malignant disease other than breast cancer within the last 5 years, with the exception of basal or squamous cell carcinoma of the skin, cervical carcinoma in situ, or low-risk cancers considered curatively treated (i.e. complete remission achieved at least 2 years prior to first dose of study drugs AND additional therapy not required while receiving study treatment).
- 5. All subjects with brain metastases, except those meeting the following criteria:
  - Brain metastases that have been treated locally and are clinically stable for at least 2 weeks prior to enrollment
  - No history of intracranial or spinal cord hemorrhage
  - No evidence of interim CNS disease progression
  - Metastasis to the midbrain, pons, and medulla
  - No ongoing neurological symptoms that are related to the brain localization of the disease (sequelae that are a consequence of the treatment of the brain metastases are acceptable.
  - Subjects must be either off steroids or on a stable or decreasing dose of ≤ 10 mg daily prednisone (or equivalent)

- 6. Receipt of any organ transplantation including allogeneic stem-cell transplantation.

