### 5. REGISTRATION PROCEDURES

### 5.1. Guidelines for VICC and Participating Institutions

Prior to registration, a copy of the IRB approval at the site will be requested and kept on file at the Vanderbilt-Ingram Cancer Center (VICC) Coordinating Center. Eligible participants will be entered on study centrally at the VICC Coordinating Center. All sites should email the Coordinating Center at [contact] to verify treatment availability prior to enrollment.

All patients MUST be registered with the VICC prior to the start of protocol treatment. Registration can only be conducted during the business hours of 8AM - 5PM Monday through Friday.

- 1) All sites should email the VICC CTSR Coordinating Center at [contact] to notify of upcoming registration and slot availability.
- 2) If a subject ID number is required prior to patient enrollment (i.e. screening tissue to be collected), the site must submit the following documents with their email notification to the Coordinating Center:
  - Copy of the patient's signed and dated Informed Consent including documentation of the consent process.
  - HIPAA authorization form (if separate from the main consent form)
  - VICC Patient Enrollment Form

The Coordinating Center will then provide a subject ID number via email.

- 3) After following your site's eligibility verification procedures, email the following documents to the VICC Coordinating Center for sponsor eligibility review and patient enrollment ([contact]):
  - Copy of the patient's signed and dated Informed Consent, including documentation of the consent process.
  - HIPAA authorization form (if separate from the main consent form)
  - VICC Patient Enrollment Form
  - Copies of laboratory, imaging and pathology reports
  - Tissue Block Registration Form (see the **Lab Manual**)
  - Completed Eligibility Checklist, including all supporting source documents. To be eligible for registration to the study, the participant must meet each inclusion and exclusion criterion listed in the eligibility checklist.

Note: VICC Coordinating Center requests 24-48 hours to review all documents and confirm eligibility. Same day treatment registrations will only be accepted with prior notice and discussion with the Coordinating Center. Please email the Coordinating Center if enrollment is needed sooner.

Once registration/enrollment confirmation from Coordinating Center is received, proceed with protocol procedures.

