#### Note:

- ☐ Additional tests may be performed at the discretion of the treating investigator as clinically indicated.
- The sample collection schedules outlined above are based on an ideal subject. The sample schedule should be followed as closely as is realistically possible; however, the schedule may be modified (± 4 business days) due to problems such as scheduling delays or conflicts (e.g., clinic closure, poor weather conditions, vacations, etc.).
- □ Items highlighted in grey are performed for research purposes (not standard of care)
  - 1. Within 4 weeks prior to starting treatment, unless otherwise noted.
  - 2. Serum chemistry includes measurement of sodium, potassium, chloride, bicarbonate, BUN, creatinine, glucose, total bilirubin, calcium, total protein, albumin, AST, ALT, and alkaline phosphatase.
  - 3. On days of Atezolizumab treatment, Pre-Dose vitals should respectively be recorded ≤ 60 minutes prior to the start of the Atezolizumab infusion. Post-Dose vitals should be recorded during and after infusion only if clinically indicated.
  - 4. Baseline evaluation of disease status by CT or MRI within 28 days prior to first dose of study drugs. Baseline and subsequent scans to include imaging of the chest, abdomen and pelvis. The first scheduled re-scan should be performed and evaluated 7 to 8 weeks after Cycle 1, Day 1 treatment, with subsequent scheduled scans intended every ~ 8 thereafter. Scanning on the same day as dosing is discouraged but allowed, provided scan results receive appropriate evaluation prior to study

- treatment. Additional disease evaluations or increased scan frequency may be performed according to the medical judgment of the patient's study physician.
- 5. Fresh biopsy in consenting patients (including those with pre-existing archival tissue) with primary or metastatic lesion judged amenable to medically safe excisional, incisional or core needle biopsy.
- 6. A 1-month follow-up clinic visit is intended 28 days (±7 days) after the preceding End-of-Treatment visit. Documented attempt(s) should be made for patient return to the study clinic. It will not be considered a protocol deviation if the patient is physically unable to return for the follow-up visit; such circumstance should be recorded in the study documents, and as much of the follow-up information as possible should be obtained via feasible patient contact and from local and outside facilities.

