#### 8.2.1.7. Hemorrhage

Hemorrhage, including major hemorrhages, defined as symptomatic bleeding in a critical area or organ, can occur with cobimetinib. In clinical studies with cobimetinib, events of cerebral hemorrhage, GI tract hemorrhage, reproductive tract hemorrhage, and hematuria have been reported. Caution should be used in patients with additional risk factors for bleeding, such as brain metastases, and in patients that use concomitant medications that increase the risk of bleeding (including antiplatelet or anticoagulant therapy).

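### Exclusion 5 makes brainstem metastasis a condition for admitting a patient with brain metastases, apparently because a No was left out

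*Combined protocol and SAP*

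**What the plan says.** Criterion 5 in Section 4.2 opens with "All subjects with brain metastases, except those meeting the following criteria", so every bullet beneath it is a requirement for admission. Six bullets follow:

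1. Local treatment, with clinical stability for at least 2 weeks before enrollment.
2. "No history of intracranial or spinal cord hemorrhage"
3. "No evidence of interim CNS disease progression"
4. "Metastasis to the midbrain, pons, and medulla"
5. "No ongoing neurological symptoms that are related to the brain localization of the disease", with an allowance for sequelae of treatment.
6. Off steroids, or on a stable or falling dose of no more than 10 mg prednisone a day.

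The exclusion list in the synopsis has the same six bullets, with the fourth worded identically. Section 5.1 says how the criteria are applied at registration: "the participant must meet each inclusion and exclusion criterion listed in the eligibility checklist".

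**The concern.** The fourth bullet asks for the very feature one would expect it to forbid. The other five all pick out lower-risk patients: treated, stable, no bleed, no progression, no symptoms, little or no steroid. A requirement for disease in the brainstem does not belong with them.

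Two things are at stake. Patients for whom the exception was evidently written may be turned away, and a site could take brainstem disease as acceptable. In a multicenter trial, sites may also resolve the contradiction differently, some reading in the missing word and some not. The criterion bears on safety: Section 8.2.1.7 reports cerebral hemorrhage in cobimetinib studies and advises "Caution should be used in patients with additional risk factors for bleeding, such as brain metastases".

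**Working it through.** No figure in the plan depends on this point, so the check is textual.

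**Form of the bullets.** Of the six, four name an adverse feature (hemorrhage, interim CNS progression, brainstem site, ongoing neurological symptoms) and two are positive requirements (local treatment with stability, steroid limit). Of the four adverse ones, three begin with No and one, the brainstem site, does not: 3 + 1 + 2 = 6. The odd one out stands directly between two of the negated bullets.

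**Could it be a fault of text extraction?** Unlikely. The same unnegated wording occurs in two separate places, the synopsis and Section 4.2. One slip copied from one to the other explains this better than the same word being lost twice.

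**Does anything else settle the intent?** No other part of the protocol states a rule on brainstem metastases.

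**What each wording does.** Take a patient with brain metastases who meets the other five bullets:

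| Site of brain metastases | As written, all three sites required | As written, any site suffices | No added, *and* changed to *or* | Bullet deleted |
|---|---|---|---|---|
| Outside the brainstem only | Excluded | Excluded | Admitted | Admitted |
| One or two of the three brainstem sites | Excluded | Admitted | Excluded | Admitted |
| All three brainstem sites | Admitted | Admitted | Excluded | Admitted |

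The first row shows the fault most clearly. On either literal reading the lower-risk patient is kept out, and both possible corrections let that patient in. The second row shows why the conjunction matters: with No added but *and* kept, the bullet could be read as barring only patients with disease at all three sites.

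**Who is affected.** Note 4 to the Study Calendar (Section 6) says "Baseline and subsequent scans to include imaging of the chest, abdomen and pelvis". Brain imaging is not listed as mandatory at screening, so the criterion will probably be applied mainly to patients whose brain metastases are already known. The documents do not say how many that may be.

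**The case against.** The strongest reply is that this is an obvious slip with little practical effect.

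- **The literal effect is mainly restrictive.** Read strictly, the bullet requires disease at all three sites and so bars almost every patient with brain metastases, which is the safer direction. A patient with brainstem disease would still have to meet the other five bullets, pass the study physician's judgment under exclusion 20 and clear central eligibility review under Section 5.1. This stands as a limit on the risk of unsafe entry. It does not help the patients wrongly kept out: exclusion 20 can only exclude further, and central review is meant to apply the written rule.
- **The hemorrhage section is general.** Section 8.2.1.7 concerns cobimetinib only and says nothing about brainstem location, and the bullet that deals with prior bleeding is worded correctly. This is fair. The section shows why the conditions for admitting these patients should be right, but it does not show that brainstem lesions carry extra risk.
- **The checklist has not been seen.** Section 5.1 points to an eligibility checklist that is not among the documents, and it may carry correct wording. That is possible, but the protocol text would still be wrong.
- **Clinicians would read it sensibly.** Exclusions 2 and 3 are also phrased as inclusion statements and need a purposive reading. For exclusion 2, however, the design summary in Section 1 confirms the meaning. Nothing does so for criterion 5.
- **The intent is inferred.** This also stands. A missing No is the best explanation but not an established one, so the sponsor should confirm it. If the bullet was meant as a permission, it still does not fit a list of conditions that must all be met.

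None of these points supplies a reading under which the bullet is correct as it stands.

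**Conclusion.** The concern holds. As written, criterion 5 treats brainstem metastasis as a condition of entry and shuts out patients with treated, stable disease elsewhere in the brain. It is certain from the text that the bullet is wrong as worded. That the cause is an omitted No is a well-supported inference from the neighboring bullets.

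The scale is limited to patients with brain metastases who meet the other five bullets, an unknown and possibly small number. No effect on the design's operating characteristics follows, and no wrongly admitted or wrongly barred patient has been shown. The sponsor should still correct it, because it is a safety-relevant entry rule that says the opposite of its apparent purpose.

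**What to change.** Confirm with the sponsor whether brainstem metastases are meant to bar entry.

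- **If they are**, begin the bullet with No and change *and* to *or*, so that disease at any one of the three sites excludes. Do this in Section 4.2 and in the synopsis.
- **If they are not**, delete the bullet in both places.

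Make the same change in the eligibility checklist if it repeats the wording. That it does so is an assumption.

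The cost is one added word and one changed word in two places, or one deleted bullet in two places, plus the checklist if needed. It can go into the next amendment. Design, sample size and analysis stay as they are.

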### 4.3. Inclusion of Underrepresented Populations

Individuals of all races and ethnic groups are eligible for this trial. There is no bias towards age or race in the clinical trial outlined.

### 5. REGISTRATION PROCEDURES

### 5.1. Guidelines for VICC and Participating Institutions

Prior to registration, a copy of the IRB approval at the site will be requested and kept on file at the Vanderbilt-Ingram Cancer Center (VICC) Coordinating Center. Eligible participants will be entered on study centrally at the VICC Coordinating Center. All sites should email the Coordinating Center at [contact] to verify treatment availability prior to enrollment.

All patients MUST be registered with the VICC prior to the start of protocol treatment. Registration can only be conducted during the business hours of 8AM - 5PM Monday through Friday.

- 1) All sites should email the VICC CTSR Coordinating Center at [contact] to notify of upcoming registration and slot availability.
- 2) If a subject ID number is required prior to patient enrollment (i.e. screening tissue to be collected), the site must submit the following documents with their email notification to the Coordinating Center:
  - Copy of the patient's signed and dated Informed Consent including documentation of the consent process.
  - HIPAA authorization form (if separate from the main consent form)
  - VICC Patient Enrollment Form

The Coordinating Center will then provide a subject ID number via email.

- 3) After following your site's eligibility verification procedures, email the following documents to the VICC Coordinating Center for sponsor eligibility review and patient enrollment ([contact]):
  - Copy of the patient's signed and dated Informed Consent, including documentation of the consent process.
  - HIPAA authorization form (if separate from the main consent form)
  - VICC Patient Enrollment Form
  - Copies of laboratory, imaging and pathology reports
  - Tissue Block Registration Form (see the **Lab Manual**)
  - Completed Eligibility Checklist, including all supporting source documents. To be eligible for registration to the study, the participant must meet each inclusion and exclusion criterion listed in the eligibility checklist.

Note: VICC Coordinating Center requests 24-48 hours to review all documents and confirm eligibility. Same day treatment registrations will only be accepted with prior notice and discussion with the Coordinating Center. Please email the Coordinating Center if enrollment is needed sooner.

Once registration/enrollment confirmation from Coordinating Center is received, proceed with protocol procedures.

Please contact the assigned Project Manager or Regulatory Coordinator with any questions regarding this process. You can also reach out to your assigned CRA once the study is activated.

The VICC Coordinating Center will assign sequence numbers to all patients in screening. Only patients deemed eligible will be registered to investigational treatment. Sequence numbers will not be re-used if a patient screen fails unless the same patient re-screens at a later point. Following registration, eligible participants should begin study treatment consistent with the protocol no later than 3 weeks after registration/enrollment by the VICC Coordinating Center. If a participant does not receive protocol therapy following registration within the allowed time period (2 weeks), the participant's registration on the study may be canceled. The assigned CRA should be notified of cancellations as soon as possible.

Issues that would cause treatment delays should be discussed with the Protocol Chair. If a participant does not receive protocol therapy following enrollment within allowed time period (2 weeks), the participant will become ineligible and will be removed from the study. Such patients will have to undergo re-screening in order to participate in the study.

As is generally accepted, standard of care procedures performed prior to consent, but within the protocol defined screening window for each assessment, can be used for study purposes. All research-only procedures must be performed after the consent date.

# 6. STUDY CALENDAR

		Week/Cycle											
Parameter	Pre- Treatment 	C1 D1	C1D8	C1 D15	C1 D1,8, 15, 22 	C2 D1	C2 D15	C3D1	D1 Every Cycle	D15 Every Cycle	Day 1 of Every Odd Cycle except Cycle 1	Every 12 weeks from C2D1 onwards	End of Treatment 
Demographics	х												
	,				CLIN	IICAL EV	ALUATION	IS:					,
History and Physical	x				x		X12		х				х
Height	х												
Vital signs and Weight 	х				х		X12		х	х			х
Performance status	х				х		X12		х				х
Ophthalmologic evaluation 	х					х						х	
				L	ABORATOR'	Y/RADIOI	LOGIC EV	LUATION	IS:	"			
Hematology (CBC/diff, plt)	х				Х		X12		х				
Comprehensive Metabolic Panel 	х			х	Х		X12		х				
Pregnancy Test 	х										х		
Phosphorus		х							х				
Uric Acid		х							х				
СРК	х								х				
Amylase/ Lipase	х										х		
Echocardiogram 	х					х						х	
Thyroid Stimulating Hormone (TSH)	х								х				
HCV antibody and HBV surface antigen	х												
TP53 status 	х												
Tumor Assessments through Imaging Studies 	х										х		

		Week/Cycle											
Parameter	Pre- Treatment 	C1 D1	C1D8	C1 D15	C1 D1,8, 15, 22 	C2 D1	C2 D15	C3D1	D1 Every Cycle	D15 Every Cycle	Day 1 of Every Odd Cycle except Cycle 1	Every 12 weeks from C2D1 onwards	End of Treatment 
			•		TREAT	MENT A	OMINISTRA	TION		•		•	
Atezolizumab			IV once every 2 weeks starting on Cycle 1 Day 15										
Cobimetinib ( TP53 -mut arm)			PO once daily from Day 1 – 21 starting on Cycle 1 Day 1										
ldasanutlin ( TP53- wt arm)		PO once daily from Day 1 – 5 starting on Cycle 1 Day 1											
					COF	RRELATI	/E STUDIE	S:					
Tumor Biopsy 	х			х									
Blood collection 		х		х				х					х
ADDITIONAL INFORMATION:						·							
Concomitant Medications Review		х							х	х			х
Adverse Events Assessment							X (AE will	be assess	sed through	hout the st	udy)		

#### Note:

- ☐ Additional tests may be performed at the discretion of the treating investigator as clinically indicated.
- The sample collection schedules outlined above are based on an ideal subject. The sample schedule should be followed as closely as is realistically possible; however, the schedule may be modified (± 4 business days) due to problems such as scheduling delays or conflicts (e.g., clinic closure, poor weather conditions, vacations, etc.).
- □ Items highlighted in grey are performed for research purposes (not standard of care)
  - 1. Within 4 weeks prior to starting treatment, unless otherwise noted.
  - 2. Serum chemistry includes measurement of sodium, potassium, chloride, bicarbonate, BUN, creatinine, glucose, total bilirubin, calcium, total protein, albumin, AST, ALT, and alkaline phosphatase.
  - 3. On days of Atezolizumab treatment, Pre-Dose vitals should respectively be recorded ≤ 60 minutes prior to the start of the Atezolizumab infusion. Post-Dose vitals should be recorded during and after infusion only if clinically indicated.
  - 4. Baseline evaluation of disease status by CT or MRI within 28 days prior to first dose of study drugs. Baseline and subsequent scans to include imaging of the chest, abdomen and pelvis. The first scheduled re-scan should be performed and evaluated 7 to 8 weeks after Cycle 1, Day 1 treatment, with subsequent scheduled scans intended every ~ 8 thereafter. Scanning on the same day as dosing is discouraged but allowed, provided scan results receive appropriate evaluation prior to study

- treatment. Additional disease evaluations or increased scan frequency may be performed according to the medical judgment of the patient's study physician.
- 5. Fresh biopsy in consenting patients (including those with pre-existing archival tissue) with primary or metastatic lesion judged amenable to medically safe excisional, incisional or core needle biopsy.
- 6. A 1-month follow-up clinic visit is intended 28 days (±7 days) after the preceding End-of-Treatment visit. Documented attempt(s) should be made for patient return to the study clinic. It will not be considered a protocol deviation if the patient is physically unable to return for the follow-up visit; such circumstance should be recorded in the study documents, and as much of the follow-up information as possible should be obtained via feasible patient contact and from local and outside facilities.
- 7. If a patient discontinues the study for reason other than progressive disease confirmed by CT or MRI (e.g. adverse event), then CT or MRI scans of the chest, abdomen and pelvis should be continued every 8-9 weeks until disease progression is confirmed by imaging.
- 8. For tissue collection, refer to Lab Manual for details of collection, processing and shipping.
- 9. For peripheral blood, refer to **Lab Manual** for details of collection, processing and shipping
- 10. Please note on Section 10 and Lab Manual that both FFPE and fresh tissue should be obtained.
- 11. Complete ophthalmologic exams will be performed prior to treatment initiation, cycle 2 day 1 (± 1 week), and every 12 weeks from then on (± 2 weeks) on patients in the cobimetinib arm only. Complete ophthalmologic examination will be performed and interpreted by a qualified ophthalmologist, including visual acuity testing, intraocular pressure measurements by tonometry, slit-lamp ophthalmoscopy, indirect ophthalmoscopy, and spectral domain optical coherence tomography. Ophthalmologic examination may be performed up to 42 days prior to starting study treatment.
- 12. For patients on the phase Ib portion of the study only (idasanutlin arm only)
- 13. Only for women of childbearing potential
- 14. Evaluation of LVEF by Echocardiogram should be performed prior to treatment initiation, cycle 2 day 1 (± 1 week), and every 12 weeks from then on (± 2 weeks) on patients in the cobimetinib arm only. The treatment discontinuation visit evaluation of LVEF does not need to be performed at the treatment discontinuation visit if an evaluation has been performed within the last 12 weeks and there are no clinically significant findings and/or changes from baseline. All patients restarting treatment with a dose reduction of cobimetinib because of a decrease in LVEF should have LVEF measurements taken after approximately 2 weeks, 4 weeks, 10 weeks, and 16 weeks, and then resume monitoring of LVEF every three treatment cycles. Any patient who develops clinical signs or symptoms suspicious of cardiac failure should undergo an LVEF assessment.
- 15. *TP53* mutation status may be known based on previously checked NGS or cfDNA commercially available assays. If not known, an archival FFPB should be sent to the Sponsor (see Section 10 and **Lab Manual**) for *TP53* mutation status determination.

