# \*\*Specimens should be mailed to arrive from Monday 8AM through Friday 1PM\*\*

## 10.3. Tissues Samples

At screening: patients will provide a signed informed consent form prior to any study related activities. Patients with known *TP53* mutation status (by previously performed NGS or cfDNA) will not be required to wait to initiate study treatment provided all other screening procedures have been completed. For patients without known *TP53* mutation status, an archival tissue (FFPE from primary or metastatic lesion) should be sent to the Sponsor (see sections 10.3.1 – 10.3.3 for details on tissue submission requirements and testing procedures), and once tissue is received, results for *TP53* status will take an average of 2 weeks and will be communicated to the site.

On study: Fresh tumor biopsies will be collected in patients (a) prior to initiating Cobimetinib or Idasanutlin (PRE-Bx), and (b) after 15 days of Cobimetinib or Idasanutlin but prior to adding on Atezolizumab (POST-Bx). One tumor core will be fixed for IHC analysis, while two additional cores will be snap-frozen for RNA and DNA extraction where feasible. The fresh biopsies will follow guidelines as listed in the **Lab Manual**. The molecular correlates for each biological sample/time point are listed below.

Correlate	Sample Source	Test	Needs immediate specialized processing	Needs immediate shipping
TILs				
CD8				
CD4				
HLA-A (MHC-I)	FFPE tumor			
IHC	biopsy	IHC/multiplexed IF		
HLA-DR (MHC-II)	Diopsy		NO	NO
IHC				
FoxP3				
PD-L1				
RNA-seq	Fresh frozen	RNA		
Exome-seq	tumor biopsy	DNA		

Parameter	Prior to Cycle 1 Day 1	Cycle 1 Day 15
Immunohistochemistry (IHC) Analysis	X	X
RNA-seq	X	X
Exome-seq (tumor)	X	
TCR Sequencing	X	X

Tissue specimen labeling, documentation and shipment

- Label ALL specimens before freezing
- If sample comes in contact with contaminate, make note in information section of paperwork.
- Enter time core biopsy was collected on paperwork.
- Label each collection containers with Patient ID sequence number/code letter, Medical Record #, site and location of biopsy, date and time.
- Ship specimens along with Tissue/Blood Registration Form directly to:

[name]. Ph.D [name] [name] Office [contact]

Research Lab [contact]

The specimens will be logged in as a consented specimen and either be stored frozen or as paraffin-embedded tissue and available for molecular pathology studies.

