#### 12.4. **Response Criteria**

### 12.4.1. Target lesions

When more than one measurable lesion is present at baseline all lesions up to a maximum of five lesions total (and a maximum of two lesions per organ) representative of all involved organs should be identified as target lesions and will be recorded and measured at baseline. This means that in instances where patients have only one or two organ sites involved, a maximum of two and four lesions, respectively, will be recorded.

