### 12.4.1.1. Evaluation of Target Lesions

Complete Response (CR): Disappearance of all target lesions. Any pathological lymph nodes (whether target or non-target) must have reduction in short axis to <10 mm.

Partial Response (PR): At least a 30% decrease in the sum of diameters of target lesions, taking as reference the baseline sum diameters.

Progressive Disease (PD): At least a 20% increase in the sum of diameters of target lesions, taking as reference the smallest sum on study (this includes the baseline sum if that is the smallest on study). In addition to the relative increase of 20%, the sum must

also demonstrate an absolute increase of at least 5 mm. (Note: the appearance of one or more new lesions is also considered progression).

Stable Disease (SD): Neither sufficient shrinkage to qualify for PR nor sufficient increase to qualify for PD, taking as reference the smallest sum of diameters while on study.

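### Research biopsies may be excisional and are not kept off target lesions, so removing one after the baseline scan could be scored as tumour shrinkage

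*Combined protocol and SAP*

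**What the plan says.** **Sampling.** Fresh biopsies are taken before treatment (PRE) and at Cycle 1 Day 15, before atezolizumab (POST). Study Calendar note 5 covers a primary or metastatic "lesion judged amenable to medically safe excisional, incisional or core needle biopsy". Section 10.3 describes a narrower procedure: "One tumor core will be fixed for IHC analysis, while two additional cores will be snap-frozen for RNA and DNA extraction where feasible". It refers sites to a Lab Manual for further guidance.

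**Timing.** Note 1 puts pre-treatment procedures "Within 4 weeks prior to starting treatment, unless otherwise noted". Note 4 asks for "Baseline evaluation of disease status by CT or MRI within 28 days prior to first dose of study drugs". The order of the PRE biopsy and the baseline scan is not set. Note 4 continues: "The first scheduled re-scan should be performed and evaluated 7 to 8 weeks after Cycle 1, Day 1 treatment".

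**Scoring.** Section 12.4.1 selects target lesions as follows: "When more than one measurable lesion is present at baseline all lesions up to a maximum of five lesions total", with at most two per organ. It makes no exception for a lesion chosen for biopsy. Section 12.4.1.1 defines target-lesion complete response as "Disappearance of all target lesions" and partial response as a fall of at least 30% in the sum of diameters from baseline. Progression is a rise of at least 20% and at least 5 mm over the smallest sum on study. No rule covers a lesion removed surgically during the study.

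**A protection that exists elsewhere.** Section 7.7 bars palliative radiation to a target lesion. Nothing equivalent applies to biopsy.

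**Biomarkers.** Section 24.3.4 tests PRE-to-POST change with a paired test. Section 1 labels the CD8 change a primary parameter. No section requires both samples to come from the same lesion.

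**The concern.** RECIST reads a fall in the sum of diameters as tumour response. If a protocol procedure removes a lesion that is in the baseline sum, the fall has nothing to do with the drug. ORR is the endpoint most directly exposed. Duration of response and irRC follow from it, and PFS is touched because the reduced sum becomes the reference for later progression. Confirmation would not catch the error, since an excised lesion is still absent at the repeat scan.

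Overlap between biopsied and target lesions is plausible. Section 4.1 requires disease amenable to biopsy, and Section 12.3.2 counts superficial lesions of at least 10 mm as measurable. Such lesions are accessible and can be target lesions.

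A second, smaller issue travels with this one. After complete excision at PRE, the POST sample must come from another lesion, so the paired change mixes drug effect with differences between lesions. The same mixing can occur with cores, because there is no same-lesion rule.

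**Working it through.** **1. The plan's own figure.** Section 24.3.1 gives a two-stage design per arm: stop at 4 or fewer successes in 16, and conclude benefit at 13 or more in 33. The probability of a positive result is the sum over x = 5 to 16 of b(16, x, p) × P(X2 ≥ 13 − x), with X2 ~ Bin(17, p). At p = 0.25 it is 0.0449 and at p = 0.50 it is 0.9017. The stated 4.5% and 90% reproduce, and the point below does not alter them.

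**2. Can removal fall between the two scans?** The baseline scan precedes the first dose and the first re-scan is at weeks 7 to 8. The Day 15 biopsy always lies between them. The PRE biopsy does so only if the scan was done first.

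**3. Effect on the sum.** Assume k equal target lesions, one excised and scored as 0 mm, the rest unchanged. The change is −1/k. For the target lesions alone to reach PD against baseline at week 8, the remaining ones would have to grow by 1.2k/(k − 1) − 1.

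| k | Change in sum | Target-lesion reading | Growth of the rest needed for PD |
|---|---|---|---|
| 1 | −100% | CR | not applicable |
| 2 | −50% | PR | 140% |
| 3 | −33% | PR | 80% |
| 4 | −25% | below the PR threshold | 60% |
| 5 | −20% | below the PR threshold | 50% |

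For k = 1, overall CR also requires non-target disease to clear and tumour markers to normalise (12.4.2.1). If non-target disease persists without progression, the table in 12.4.3 gives PR. For irRC, Section 13.4 requires a confirmed fall of at least 50%, so removing one of three equal index lesions is not enough.

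**4. ORR.** One false responder adds 1/33 = 3.0 points. At the response rate of about 12% quoted in Section 3.2, 0.12 × 33 = 3.96 responders are expected, and one more gives 4.96/33 = 15.0%. Sections 2 and 12.1 restrict ORR to patients with measurable disease, so the denominator may be below 33 and the step larger.

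**5. 16-week PFS.** Assume two 20 mm target lesions, no new lesions and no non-target progression.

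- Both growing 10% per 8 weeks. Without excision: 40, 44, 48.4 mm, which is +21% and +8.4 mm at week 16 (PD). With one excised: 22 mm at week 8, then 24.2 mm (+10%), not PD. A failure becomes a success.
- Both growing 20%. Without excision: 48 mm at week 8 (+20%, +8 mm), PD. With excision: 24 mm (−40%, PR), then 28.8 mm (+4.8 mm), not PD. A failure becomes a success.
- Both growing 22%. With excision: 24.4 then 29.77 mm (+22%, +5.4 mm), PD by week 16. The binary result is unchanged. The same holds at 25% and 30%.
- The excised lesion would have stayed static; the other is static to week 8, then grows 30%. Without excision: 46 against 40 mm (+15%), not PD. With excision: 26 against a nadir of 20 mm (+30%, +6 mm), PD. A success becomes a failure.

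**6. What-if for type I error.** Suppose a share s of true 16-week failures were turned into successes and none the other way, so p = 0.25 + 0.75s. In the same formula, s = 0, 2%, 5% and 10% give 4.5%, 6.8%, 11.6% and 23.6%. Every s is an assumption; the documents give no basis for any of them.

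**The case against.** The strongest reply is that excision is not the planned technique. Section 10.3 describes cores, and note 5 may only be listing kinds of accessible lesion. The Lab Manual, which is not among the documents, may restrict technique or lesion choice. This stands as a reason to expect few cases. It does not remove the option that note 5 leaves open, and the two places should agree.

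Several stronger readings are tempting, and the documents do not support them.

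- **That excision is scored as response.** The documents do not say how an excised lesion is scored. The 12.4.3 table has a row for target lesions not all evaluated, which gives NE, and a site could use it. The gap is that scoring is unspecified and sites could differ.
- **That the biopsied lesion must be a target lesion.** Measurable disease is not an inclusion criterion. An accessible lesion may be non-target: a small lesion or node (12.2.2), blastic bone (12.2.4), a previously treated lesion (12.3), or a third lesion in one organ.
- **That the biopsies always follow the baseline scan.** This holds for Day 15 only. A lesion excised before the scan creates no response artefact.
- **That the trial's type I error is inflated.** The what-if figures assume one-way misclassification at invented rates. Progression is judged from the nadir, new lesions and non-target progression still count, and step 5 shows the error can run in either direction.
- **That POST can never sample the PRE lesion.** This is true only after complete excision at PRE.

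**Conclusion.** The concern holds in a limited form. The protocol permits a research procedure that can remove a target or index lesion after the baseline scan, and has no rule for scoring what follows. Read literally, Sections 12.4.1 and 12.4.1.1 could record the removal as shrinkage, enough alone for target-lesion partial response with up to three equal target lesions.

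The size is at least 3 points of ORR per affected patient at 33 patients. This assumes equal lesions, no other change and an excised lesion scored as 0 mm. For 16-week PFS the effect is smaller and of mixed direction; the two-stage design and its stated error rates are unaffected as designed. Frequency is unknown and probably low, given Section 10.3. Because an affected patient would be misread on a secondary efficacy endpoint and the remedy is wording, the change should be made.

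**What to change.** - Reconcile note 5 with Section 10.3, and state that target lesions and irRC index lesions are not to be excised for research sampling. Where a non-target lesion is available, prefer it for biopsy.
- In Sections 12.4.1 and 13.3, state that any lesion excised during the study is left out of the baseline sum and all later sums, so that every site scores it the same way.
- Record the identity of the sampled lesion at PRE and POST in the eCRF, and sample the same lesion where feasible.
- Keep all PRE/POST pairs in the main biomarker analysis and report same-lesion pairs as a sensitivity analysis. Making them the main set would shrink an already small sample.

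The cost is protocol wording and one or two eCRF fields. Sample size, type I error and power do not change. Slightly fewer biopsies would be obtained, from patients whose only accessible lesion is a target suitable only for excision.
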